10.2 Response Criteria

The neurologic examination and the MRI or contrast-enhanced CT at each evaluation will be scored as follows:

10.2.1 Neurologic Exam Status

Table 12. Neurologic Exam Status as Compared to Pre-Treatment Exam

Status	Criteria
Better	No new neurologic deficits. Must be on stable or decreasing dose of steroids, with stable to improved ECOG performance status
Worse	New neurologic deficits, declining ECOG performance status, or requiring increasing dose of steroids to remain stable

10.2.2 MRI Assessment: Based on Response Assessment in Neuro-Oncology working group (RANO) criteria [\(37\)](#).

Table 13. RANO Criteria

Response	Criteria
Complete Response	Requires all of the following: Complete disappearance of all enhancing measurable and non-measurable disease sustained for at least 4 weeks; no new lesions; stable or improved non-enhancing (T2/FLAIR) lesions; and with patient off corticosteroids or only on physiological replacement doses. Requires repeat MRI in 4 weeks for confirmation.
Partial Response	Requires all of the following: $\geq 50\%$ decrease, compared with baseline, in the sum of products of perpendicular diameters of all measurable enhancing lesions sustained for at least 4 weeks; no progression of non-measurable disease; no new lesions; stable or improved non-enhancing (T2/FLAIR) lesions on the same or lower dose of corticosteroids compared to baseline scan; and with patient on a dose corticosteroids not greater the dose at the time of baseline scan, and is stable or doing better clinically. Requires repeat MRI in 4 weeks for confirmation.
Stable Disease	Stable disease occurs if the patient does not qualify for complete response, partial response, or progression, and requires the following: Stable non-enhancing (T2/FLAIR) lesions on the same or lower dose of corticosteroids compared with baseline scan and clinically stable status. In the event that the corticosteroid dose was increased for new symptoms and signs without confirmation of disease progression on neuroimaging, and subsequent follow-up imaging shows that this increase in corticosteroids was required because of disease progression, the last scan considered to show stable disease will be the scan obtained when the corticosteroid dose was equivalent to the baseline dose.
Progressive Disease	Progression is defined as any of the following: $\geq 25\%$ increase in the sum of the products of perpendicular diameters of enhancing lesions, on stable or increasing doses of steroids; a significant increase in non-enhancing (T2/FLAIR) on stable or increasing dose of steroids compared with baseline scan or best response after initiation of therapy; the appearance of new lesions; clear progression of non-measurable lesions; definite clinical deterioration not attributable to other causes apart from tumor or to decreases in corticosteroid dose.

10.2.3 Contrast-enhanced CT Assessment: Based on Macdonald Criteria (38).

Table 14. Macdonald Criteria

Response	Criteria
Complete Response	Requires all of the following: complete disappearance of all enhancing measurable and non-measurable disease sustained for at least 4 weeks; no new lesions; no corticosteroids; and stable or improved clinically.
Partial Response	Requires all of the following: $\geq 50\%$ decrease compared with baseline in the sum of products of perpendicular diameters of all measurable enhancing lesions sustained for at least 4 weeks; no new lesions; stable or reduced corticosteroid dose; and stable or improved clinically.
Stable Disease	Requires all of the following: does not qualify for complete response, partial response, or progression; and stable clinically.
Progression	Defined by any of the following: $\geq 25\%$ increase in sum of the products of perpendicular diameters of enhancing lesions; any new lesion; or clinical deterioration.

*Table from (37)

10.3 Considerations for Patients with Multifocal Disease

For patients with multifocal disease, progressive disease is defined as $\geq 25\%$ increase in the sum of the products of perpendicular diameters of enhancing lesions compared with the smallest tumor measurements after the initiation of therapy. The appearance of a new lesion or unequivocal, progression of non-target lesions will also be considered progression.

Partial response is defined as a $\geq 50\%$ decrease, compared with baseline, in the sum of products of perpendicular diameters of all measurable enhancing lesions sustained for at least 4 weeks, with stable or decreasing corticosteroid dose and with stable neurologic exam.

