10.4.1 Duration of Response

Duration of overall response: The duration of overall response is measured from the time measurement criteria are met for a complete response or a partial response (whichever is first recorded) until the first date that recurrent or progressive disease is objectively documented (taking as reference for progressive disease the smallest measurements recorded since the treatment started).

The duration of overall complete response is measured from the time measurement criteria are first met for complete response until the first date that progressive disease is objectively documented.

Duration of stable disease: Stable disease is measured from the start of the treatment until the criteria for progression are met, taking as reference the smallest measurements recorded since the treatment started, including the baseline measurements.

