- E. If baseline history and physical exam is performed on a day other than C1D1, a brief visit to determine neurologic stability on current dose of steroids is also required on day 1 or day before.
- F. Only patients in the safety lead-in cohort.
- G. For women capable of pregnancy: pregnancy test at baseline; subsequently, review pregnancy risks and offer pregnancy test
- H. First “on-treatment” ECG is done approximately C1D8-C1D15 to evaluate acute changes relative to the study drug combination; the second is done approximately C3D1 to evaluate changes after a more chronic dosing of study drug combination.
- I. MRI or contrast-enhanced CT within 3 weeks prior to enrollment. An MRI is the preferred modality in all patients without a contraindication to MRI. Baseline and follow-up scans must be performed using the same modality.
- J. Imaging to be done to assess response every 2 months from initiation of treatment until off-study due to patient withdrawal, progression, or death. If MRI or contrast-enhanced CT shows response then repeat after 1 month to confirm response and then follow every 2 months from time of confirmatory MRI or CT. Patients with symptoms suggestive of progression may have imaging done between regularly scheduled scans, any time there is clinical concern for progressive disease. See also Section [10.4](#).
- K. See Section [7.8](#): After stopping study treatment, capture initiation of new therapy, first new progression date, and/or survival status since last observation approximately every 2 months during extended follow-up.
- L. Obtain and analyze archived tumor tissue per Section [11](#). During enrollment of the initial PDGFR α -unselected subgroup (prior to first interim analysis), archived tumor tissue must be obtained and analyzed, but analysis does not need to be performed prior to enrollment. After the first interim analysis, if the study proceeds to include only PDGFR α -positive patients, archived specimen analysis for PDGFR α will be required, and results must be known, prior to enrollment.
- M. Sodium, potassium, carbonate, chloride, glucose, calcium, BUN, creatinine.
- N. Additional assessments may be done at investigator discretion in patients with congestive heart failure, bradyarrhythmias, those on drugs known to prolong the QT interval, including Class Ia and III antiarrhythmics, and electrolyte abnormalities.
- O. ALT, AST, ALP, total bilirubin, direct bilirubin, albumin, total protein.

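### Section 10.3 leaves the baseline scan out of the multifocal progression reference, conflicts with 10.4.1, and does not say whether it adds to or replaces Tables 13 and 14, so some growth over baseline could be scored as 6-month PFS.

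*Combined protocol and SAP*

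**What the plan says.** Four places in the protocol bear on when measured growth counts as progression.

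- **Section 10.3 (multifocal disease).** The 25% increase is judged "compared with the smallest tumor measurements after the initiation of therapy". A further sentence adds: "The appearance of a new lesion or unequivocal, progression of non-target lesions will also be considered progression". Partial response needs a 50% decrease held for 4 weeks, with conditions on steroids and the neurologic exam; T2/FLAIR is not mentioned.
- **Section 10.4.1 (duration of stable disease).** Progression is judged "taking as reference the smallest measurements recorded since the treatment started, including the baseline measurements".
- **Table 13 (RANO, MRI).** The size clause is a 25% "increase in the sum of the products of perpendicular diameters of enhancing lesions, on stable or increasing doses of steroids", with no reference scan of its own. The next clause, on T2/FLAIR, is the one that carries "compared with baseline scan or best response after initiation of therapy". The table also counts "definite clinical deterioration not attributable to other causes apart from tumor or to decreases in corticosteroid dose". Its partial response requires "no progression of non-measurable disease; no new lesions; stable or improved non-enhancing (T2/FLAIR) lesions".
- **Table 14 (Macdonald, CT).** A 25% increase counts as progression, with no reference scan named.

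The baseline scan is an "MRI or contrast-enhanced CT within 3 weeks prior to enrollment" (Study Calendar, note I), so it is not a measurement made after therapy starts. Response is reassessed every 8 weeks (10.4). The primary endpoint (3.2) takes progression from RANO or Macdonald criteria and does not name 10.3. Section 10.4.2 counts symptomatic as well as radiographic progression.

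**The concern.** At the first on-treatment scan, the only measurement that 10.3 admits as a reference is that scan itself. However much the tumor has grown since baseline, the size criterion cannot be met there, and the enlarged tumor then becomes the reference for later scans. The same patient can be progressive under 10.4.1 and not under 10.3.

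Six-month PFS is a yes/no outcome judged on small counts: 4 of 16 to continue, 11 of 33 to succeed (13.2). The stage 1 count also decides whether enrollment narrows to PDGFRα-positive tumors (13.1). One patient scored differently can matter, and the trial is open-label with one arm, so a definition left to choice would be settled by people who know the outcomes.

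The response side has a related gap. A multifocal patient whose enhancing disease halves while T2/FLAIR disease clearly grows meets 10.3's partial response and Table 13's progression. That affects the response rate, a secondary endpoint.

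**Working it through.** **1. The plan's own figures (13.2).** Null rate 0.20, alternative 0.40; stop at 3 or fewer of 16; success at 11 or more of 33. The probability of success is the sum, over stage 1 counts x from 4 to 16, of P(X1 = x) × P(X2 ≥ 11 − x), with X1 binomial on 16 patients and X2 on 17. This gives 0.0475 at 0.20 and 0.811 at 0.40, so the stated 5% and 80% are met. The design itself is not in dispute.

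**2. Steady compound growth.** Scans at weeks 8, 16 and 24; growth g per 8 weeks; baseline set to 1.
- Baseline included: progression by week 24 if (1 + g)³ ≥ 1.25, so g ≥ 1.25^(1/3) − 1 = 7.7%.
- Literal 10.3: the reference is the week 8 scan, so (1 + g)² ≥ 1.25 and g ≥ 1.25^(1/2) − 1 = 11.8%.
- The two readings disagree on 6-month status only between these values. Growth hidden at week 24 is at most just under 1.118³ − 1 = 40%.

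For linear growth of d (share of baseline) per 8 weeks, the limits are 0.25/3 = 8.3% and 0.25/1.75 = 14.3%, with at most 3 × 14.3% = 43% hidden.

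| Growth per 8 weeks | Progression, baseline included | Progression, literal 10.3 |
|---|---|---|
| 7% | not by week 24 | not by week 24 |
| 10% | week 24 | not by week 24 |
| 15–20% | week 16 | week 24 |
| 25–50% | week 8 | week 16 |

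Above the band, literal 10.3 dates progression one scan late, but the patient is still a 6-month failure, assuming that the week 24 scan is done and counts.

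**3. Front-loaded growth.** Take sums of 10, 14, 17 and 17.4. Against baseline, week 8 is 14/10 = +40%, which is progression. Under literal 10.3, week 16 is 17/14 = +21% and week 24 is 17.4/14 = +24%, so the size criterion is never met although the tumor is 74% above baseline. A series of 1.0, 2.0, 2.2, 2.4 also escapes: +140% over baseline, +20% over week 8.

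**4. Effect on the test, illustrative only.** Let f be the multifocal share and m the share of multifocal true failures scored as successes. The documents give neither. If multifocal patients fail at the same 80% rate, the apparent null rate is 0.20 + 0.80 × f × m.

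| f | m | Apparent rate | P(success) |
|---|---|---|---|
| 10% | 10% | 0.208 | 0.061 |
| 10% | 25% | 0.220 | 0.085 |
| 20% | 10% | 0.216 | 0.076 |
| 20% | 25% | 0.240 | 0.138 |

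In patients, f = 10% of 33 with 80% failing is 2.64 failures; hiding 10% to 25% of them moves 0.26 to 0.66 of one patient.

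**The case against.** The strongest reply is that 10.3 does not stand alone. It is headed as considerations, nothing in it says that it displaces Tables 13 and 14, and the primary endpoint cites RANO or Macdonald. Both tables carry their own 25% criterion, 10.4.1 includes baseline, and a sensible reader would apply the baseline-inclusive rule. This stands in part: it makes the problem a conflict between sections rather than a rule certain to hide growth. It does not remove the conflict, because 10.3 is worded as a definition and neither table clearly names a reference for enhancing growth.

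A reader might infer that growth at the first scan can never be progression. The documents do not support that: a new lesion or non-target progression counts under 10.3 itself, and symptomatic progression counts under 10.4.2. A reader might also infer that steadily growing tumors generally pass as 6-month successes. They do not; only the narrow band in the working does, and the series reaching 74% is front-loaded (+40%, +21%, +2%).

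Other gaps look larger than they are. That 10.3's partial response does not rule out new lesions has little effect, since a new lesion is progression in the same section. That its progression rule omits clinical deterioration has little effect on PFS, because of 10.4.2. Loss of nadir as the reference is largely met by 10.4.1, which uses the smallest measurement for the duration of both response and stable disease. The T2/FLAIR mismatch remains, if 10.3 is read as replacing Table 13.

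**Conclusion.** The concern holds as an internal inconsistency that can alter the primary endpoint. Section 10.3 omits baseline, conflicts with 10.4.1, and leaves its relation to Tables 13 and 14 unstated. Followed literally, it would score as 6-month PFS those multifocal patients with front-loaded growth, or with steady growth of about 7.7% to 11.8% per 8 weeks, who have no new lesion, non-target progression or symptomatic progression. That rests on scans at weeks 8, 16 and 24 and on reading 10.3 as the governing rule.

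The number of patients affected cannot be derived from the documents. The rise in type I error from 0.0475 to between 0.061 and 0.138 follows from assumed shares and is not an estimate; in particular, the hidden share is not derived from any distribution of growth rates. The response-rate conflict over T2/FLAIR concerns a secondary endpoint.

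**What to change.** Reconcile 10.3, Tables 13 and 14, and 10.4.1 to a single reference for the 25% increase: the smallest sum recorded at baseline or since, as 10.4.1 already has it for stable disease. State in 10.3 that it supplements the tables and that multifocal patients must otherwise meet all their conditions, including T2/FLAIR; or delete its separate definitions. Do this before outcomes are scored.

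The cost is protocol wording only: no extra scans or patients, and no change to the sample size. Observed 6-month PFS and response rate may be slightly lower.

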10.4 Timing of Imaging Studies

For the purposes of this study, patients will be re-evaluated for response every 8 weeks. In addition to a baseline scan, confirmatory scans should also be obtained 4 weeks following initial documentation of objective response (PR or CR).

Evaluation of neurologic imaging can be confounded by factors such as edema and subtle variances in imaging parameters. In the event that imaging meets objective progression criteria, but the patient's clinical status is stable or improving, with a stable or decreasing steroid dose, and, in the opinion of the investigator, the aggregate patient assessment is not definitive for progression, study therapy can continue at investigator's discretion with repeat imaging at time of next scheduled assessment. If subsequent imaging again meets objective progression criteria, regardless of clinical and/or steroid dosing status, then progression criteria will have been met, and the date of progression will be noted as the earliest imaging date that was consistent with objective progression.

If clinical conditions raise the concern for progressive disease in between regularly scheduled interval scans, repeat imaging may be performed at the treating physician's discretion.

10.4.1 Duration of Response

Duration of overall response: The duration of overall response is measured from the time measurement criteria are met for a complete response or a partial response (whichever is first recorded) until the first date that recurrent or progressive disease is objectively documented (taking as reference for progressive disease the smallest measurements recorded since the treatment started).

The duration of overall complete response is measured from the time measurement criteria are first met for complete response until the first date that progressive disease is objectively documented.

Duration of stable disease: Stable disease is measured from the start of the treatment until the criteria for progression are met, taking as reference the smallest measurements recorded since the treatment started, including the baseline measurements.

10.4.2 PFS

PFS is defined as the duration of time from start of treatment to time of symptomatic and/or radiographic progression or death, whichever occurs first.

11 CORRELATIVE STUDIES

11.1 PDGFR α Expression in Primary Tumor Samples

Analysis will take place on archived tissue. Patients being considered for enrollment onto this study will have had primary therapy for their high-grade glioma, which includes resection, when possible, with a minimum of a core needle biopsy of the tumor for patients with unresectable disease. Some patients will also have had a biopsy of recurrent disease. Other patients will have had progression from a lower grade glioma, and multiple biopsies will be available to choose from. The preferred tumor specimen is from the primary resection specimen at the time of initial treatment for high-grade glioma.

11.2 Timing of Sample Collection and Analysis

In the initial PDGFR α -unselected cohort, archived samples may be obtained and submitted for initial processing any time after study consent is obtained, preferably within the first few weeks of study therapy. Analysis/interpretation of these samples may be done without regard to participant initiation of study treatment. Samples may be held for batch processing, staining, and analysis until such time as it is determined whether the study will proceed to enrollment of only patients known to have PDGFR α -positive tumors.

If the study continues to enrollment of a PDGFR α -positive cohort, archived samples will need to be collected, processed, and scored as part of the screening process to determine eligibility.

After the first interim analysis for 6-month PFS:

- If the study continues with enrollment of PDGFR α -unselected patients only, tissue collection, processing, and analysis may continue, with the understanding that samples may be processed and/or analyzed for PDGFR α status in a non-CLIA-certified setting. In

this case, samples will be deparaffinized in VCU Anatomic Pathology, immunostained in the VCU Massey Cancer Center Clinical and Translational Research Laboratory (VCU MCC CTRL) and scored in VCU Anatomic Pathology.

- If the study continues with enrollment of PDGFR α -selected patients (only those who have PDGFR α -positive tumors), results of PDGFR α immunostaining will need to be available PRIOR TO enrollment. Immunostaining for the PDGFR α -positive cohort will be performed in a CLIA-certified setting. In this case, for consistency, all previously collected samples from the PDGFR α -unselected patient cohort will also undergo staining and analysis in the CLIA-certified setting.

11.3 Collection of Specimens

A total of 5 unstained slides, each with specimen 4-microns thick, should be obtained. All slides will have PHI removed before submission for correlative testing and will be labeled with:

- Study Number
- Subject ID#
- Surgical pathology accession #

VCU MCC CTRL and VCU Anatomic Pathology will maintain logs of samples handled for correlative testing keyed by those 3 identifiers.

To obtain a biopsy specimen from VCU archives, contact VCU Anatomic Pathology [REDACTED] and reference surgical pathology specimen number and block number. Provide a copy of protocol specifications for sample collection and signed informed consent.

- For the PDGFR α -unselected cohort, make arrangements for de-identified slides to be obtained and submitted to the VCU MCC CTRL to be stored until a determination is made about where the slides will be processed and analyzed.
- For the PDGFR α -selected cohort, make arrangements for de-identified slides to be obtained and submitted to the VCU Anatomic Pathology for pre-enrollment processing and analysis to determine PDGFR α -status

VCU Anatomic Pathology [REDACTED]
[REDACTED]
[REDACTED]
[REDACTED]
[REDACTED]
[REDACTED]
[REDACTED]
[REDACTED]
[REDACTED]
[REDACTED]

To obtain an archived biopsy specimen from outside hospital, request that a tissue block be sent to Anatomic Pathology at the above address, Attention [REDACTED] and

notify [REDACTED] to expect the specimen for research testing. The study team should coordinate with [REDACTED] to transfer the prepared slides from outside tissue blocks to the VCU MCC CTRL.

If the outside hospital does not transfer blocks of tissue, request delivery of 5 unstained slides, each with specimen 4-microns thick, directly to the study team. Blank slides from an outside hospital do not need to be sent to pathology for preparation, and may be submitted directly to the VCU MCC CTRL for immunostaining.

11.4 Handling of Specimens

Five unstained slides, each with specimens 4 microns thick, will be submitted for immunostaining.

11.5 Immunostaining of Specimens

Immunostaining and analysis will be done in either the VCU MCC CTRL or in a CLIA-certified setting, per Section [11.2](#).

11.6 Interpretation of Correlative Study

[REDACTED]

[REDACTED]

[REDACTED]

11.7 Other Potential Pharmacodynamic Markers

The laboratory of [REDACTED] at MCC will analyze the samples for the pharmacodynamic marker studies.

12 STUDY CALENDAR

Table 15. Study Calendar

Event	Baseline ^A	On Treatment ^B									Follow Up ^C	
		Cycle 1				Cycle 2				Cycle 3+	Initial 30-Day Period	Extended Period
		D1	D8	D15	D22	D1	D8	D15	D22	D1		
Informed Consent	X ^D											
Demographics, Height	X ^D											
History and Physical Exam including Performance Status, Dermatologic and Neurologic Assessments	X	X ^E	X ^F	X	X ^F	X		X		X		
Vital Signs, Weight	X	X	X ^F	X	X ^F	X		X		X		
Baseline Symptoms	X											
Adverse Event Assessment		X	X ^F	X	X ^F	X		X		X	X ^C	
Concurrent Medications, Including Steroid Dosing Review	X	X	X ^F	X	X ^F	X		X		X		
Study Medication Diary Review and Pill Count		X	X ^F	X	X ^F	X		X		X		
Pregnancy Test, Counseling	X ^G											
ECG	X		X ^H							X ^H		
Tumor Imaging	X ^I	X ^J										
Survival, Alternative Therapies										X ^C	X ^K	
Archived Tumor Tissue	X ^L											
CBC with Differential, Platelets	X	X ^B	X ^F	X	X ^F	X		X		X		
Basic Metabolic Panel, ^{M,N} Hepatic Panel, ^O Magnesium, ^N Phosphorus ^N	X	X ^B	X ^F	X	X ^F	X		X		X		
PT, INR ^P	X	X										
Serum Valproic Acid Level ^Q	X	X										
Serum Ammonia	X											
Valproic Acid	Initiate, titrate, and/or maintain level ≥ LLN for the laboratory and dose per Sections 6 and 9 .											
Sorafenib	Initiate on C1D1, provided valproic acid level is ≥ LLN for the laboratory; continue dosing per Sections 6 and 9 .											
Sildenafil												

- A. Within 2 weeks prior to enrollment unless otherwise noted.
- B. C1D1 labs do not need to be repeated on C1D1 if done within 7 days prior to initiation of study treatment. Other C1D1 assessments may be performed within 3 days prior to day 1 dosing. In cycle 1, weekly assessments must be done within +/- 1 day of required time point. In cycle 3 and subsequent cycles, assessments must be done within +/- 3 days of scheduled time point; greater variations in timing may be permitted after cycle 2, with prior principal investigator/designee notification. For patients who are still on study for longer than 36 months, assessments may be done every other cycle (approximately every 8 weeks).
- C. See Section [7.8](#): The 30-day post-treatment follow-up period is meant to capture resolution or stabilization of ongoing treatment-related AEs or evolution of new treatment-related AEs.
- D. Within 4 weeks prior to initiation of study treatment.
- E. If baseline history and physical exam is performed on a day other than C1D1, a brief visit to determine neurologic stability on current dose of steroids is also required on day 1 or day before.
- F. Only patients in the safety lead-in cohort.
- G. For women capable of pregnancy: pregnancy test at baseline; subsequently, review pregnancy risks and offer pregnancy test
- H. First “on-treatment” ECG is done approximately C1D8-C1D15 to evaluate acute changes relative to the study drug combination; the second is done approximately C3D1 to evaluate changes after a more chronic dosing of study drug combination.
- I. MRI or contrast-enhanced CT within 3 weeks prior to enrollment. An MRI is the preferred modality in all patients without a contraindication to MRI. Baseline and follow-up scans must be performed using the same modality.
- J. Imaging to be done to assess response every 2 months from initiation of treatment until off-study due to patient withdrawal, progression, or death. If MRI or contrast-enhanced CT shows response then repeat after 1 month to confirm response and then follow every 2 months from time of confirmatory MRI or CT. Patients with symptoms suggestive of progression may have imaging done between regularly scheduled scans, any time there is clinical concern for progressive disease. See also Section [10.4](#).
- K. See Section [7.8](#): After stopping study treatment, capture initiation of new therapy, first new progression date, and/or survival status since last observation approximately every 2 months during extended follow-up.
- L. Obtain and analyze archived tumor tissue per Section [11](#). During enrollment of the initial PDGFR α -unselected subgroup (prior to first interim analysis), archived tumor tissue must be obtained and analyzed, but analysis does not need to be performed prior to enrollment. After the first interim analysis, if the study proceeds to include only PDGFR α -positive patients, archived specimen analysis for PDGFR α will be required, and results must be known, prior to enrollment.
- M. Sodium, potassium, carbonate, chloride, glucose, calcium, BUN, creatinine.
- N. Additional assessments may be done at investigator discretion in patients with congestive heart failure, bradyarrhythmias, those on drugs known to prolong the QT interval, including Class Ia and III antiarrhythmics, and electrolyte abnormalities.
- O. ALT, AST, ALP, total bilirubin, direct bilirubin, albumin, total protein.
- P. In patients taking warfarin: at baseline and then as clinically indicated.

Q. Initial level approximately 5 days after starting valproic acid. Once on study treatment, check level at least every 2 weeks, or more frequently if clinically indicated, through the end of cycle 2. After cycle 2, check only as clinically indicated.

